8.7.4. Missed or Vomited Selinexor Doses

If a dose was missed, the missed dose will be administered if the time for the next scheduled dose is \geq 72 hours. The missed dose will not be administered if the time for the next scheduled dose is $<$ 72 hours. The next dose will be taken as per the schedule.

If a dose must be skipped (e.g., due to recommendation of Investigator), the next dose will be taken as per the schedule. Doses should not be administered less than 72 hours apart and all missed and delayed doses should be documented.

If a dose is vomited within one hour of ingestion and all intact selinexor tablets are seen, it will be replaced. If vomiting occurs more than one hour after dosing, it will still be considered a complete dose.

9. DISCONTINUATION OF STUDY TREATMENT AND PATIENT DISCONTINUATION/WITHDRAWAL

9.1. Patient Discontinuation/Withdrawal from the Study

A patient may withdraw from the study at any time at his/her own request or may be withdrawn at any time at the discretion of the Investigator for safety, behavioral, compliance, or administrative reasons.

The Investigator must determine the primary reason for a patient's discontinuation of study treatment/withdrawal from the study and record this information on the eCRF.

The Investigator may remove a patient from study treatment for any of the following reasons:

- AEs or toxicity that cannot be managed by supportive care
- Misuse of study treatment (e.g., deliberate overdosing by patient)
- Any other medically appropriate reason or significant protocol violation, in the opinion of the Investigator.

The Investigator must remove a patient from study treatment for any of the following reasons:

- Patient withdraws consent to continue study treatment
- Pregnancy

9.2. Lost to Follow up

A patient will be considered lost to follow-up if he or she repeatedly fails to return for scheduled visits and is unable to be contacted by the study site.

The following actions must be taken if a patient fails to return to the clinic for a scheduled study visit:

- The site must attempt to contact the patient and reschedule the missed visit as soon as possible and counsel the patient on the importance of maintaining the assigned visit schedule and ascertain whether or not the patient wishes to and/or should continue in the study.
- Before a patient is deemed lost to follow up, the investigator or designee must make every effort to regain contact with the patient (where possible, 3 telephone calls and, if necessary, a certified letter to the patient's last known mailing address or local equivalent methods). These contact attempts should be documented in the patient's medical record.
- Should the patient continue to be unreachable, he/she will be considered to have withdrawn from the study.
- Any patient who does not withdraw from the study but who stops attending study visits and does not respond to 3 documented contact attempts will be considered lost to follow-up.

9.3. Early Termination of the Study

The study may be terminated at the sole discretion of the Sponsor for any reason, including medical or ethical reasons affecting the continued performance of the study, or difficulties in the recruitment of patients. If this occurs, the Sponsor will notify independent ethics committees (IECs), institutional review boards (IRBs), Investigators, and regulatory authorities.

10. STUDY ASSESSMENTS AND PROCEDURES

Study procedures and their timing are summarized in the Schedule of Assessments (SoA).

- Immediate safety concerns should be discussed with the Sponsor's Medical Monitor immediately upon occurrence or awareness to determine if the patient should continue or discontinue study treatment.
- Adherence to the study design requirements, including those specified in the SoA, is essential and required for study conduct.
- All screening evaluations must be completed and reviewed to confirm that potential patients meet all eligibility criteria. The Investigator will maintain a screening log to record details of all patients screened and to confirm eligibility or record reasons for screening failure, as applicable.
- Procedures conducted as part of the patient's routine clinical management (e.g., blood count) that were obtained prior to signing of the informed consent form (ICF) may be utilized for screening purposes provided the procedures met the protocol-specified criteria and were performed within the time frame defined in the SoA.
- All protocol defined assessments on clinic visit days (when study drug is given) should be completed prior to study drug dosing.

10.1. Informed Consent

Eligible patients may only be included in the study after providing written (witnessed, where required by law or regulation), IRB/IEC/research ethics board (REB)-approved informed consent (Section 13.3). Informed consent must be obtained before conducting any study-specific procedures (i.e., all procedures described in the protocol, unless performed as part of the patient's routine clinical management as mentioned above). The process of obtaining informed consent should be documented in the patient source documents.

10.2. Baseline Assessments

10.2.1. Demographics

Patient demographics (including date of birth, sex, race, ethnicity, and age at the time of consent) will be collected.

10.2.2. Medical History

A complete medical history will be obtained from each patient by at least the month and year. Medical conditions or symptoms experienced within 30 days of Screening as well as those ongoing at the time of Screening, any medical conditions that require medication will be documented. A detailed history of disease-specific diagnostic and prognostic testing and test results (such as phenotypic and cytogenetic profiles) and type of melanoma will also be collected. All prior anti-cancer therapies, and disease management, length of care, and best overall response will be documented, including the start date, end date/ongoing. Data from standard-of-care procedures including whole blood or platelet transfusion will be part of the patient's medical history and may

be used for study purposes. In addition, a complete ophthalmic history and the smoking history of the patient will be recorded.

10.3. Efficacy Assessments

10.3.1. Response criteria

Computed Tomography (CT) or Magnetic Resonance Imaging (MRI)

Disease response is based on tumor measurement using CT scans or, MRI. Scans will be performed at Screening (Day -28 to Day -1) and every 9 weeks for 6 months, then every 3 months thereafter until confirmed PD, death or consent withdrawal occurs. Scans at the EoT visit should be performed for patients who discontinue for reasons other than documented PD, if previous imaging was more than 6 weeks old. The same scan modality should be used for all assessments.

10.3.1.1. RECIST

Disease response will be assessed according to the RECIST criteria v1.1 ([Appendix 1](#)).

10.3.1.2. iRECIST

Antitumor response based on assessment of changes in tumor burden will be assessed by iRECIST ([Appendix 2](#)). The RECIST 1.1 definitions will be used to determine “immune” response: PFS and ORR.

10.5. Safety Assessments

Planned time points for all safety assessments are provided in the SoA.

10.5.1. Physical Examinations

The physical examination will be performed according to the standards at each institution.

Physical examination, including vital signs, will be performed on the scheduled days as indicated in the SoA. Physical examinations should include general appearance, dermatological, head, eyes, ears, nose, throat, respiratory, cardiovascular, abdominal, lymph nodes, musculoskeletal, and neurological examinations. Full physical examinations will be performed prior to receiving first dose of study drug and as indicated in the SoA. All other physical examinations during the study should be limited, and symptom-directed examinations.

Height (without shoes) in centimeters and weight (indoor clothing without shoes) in kilograms (kg) will be measured during the physical examinations. Any new, clinically significant findings that occur after dosing with study treatment begins will be reported as AEs.

Information about the physical examination must be present in the source documentation at the study site. The result of the physical examination prior to the start of study treatment must be included in the Relevant Medical History/Current Medical Conditions eCRF. Clinically relevant findings made after the start of study treatment, which meet the definition of an AE, must be recorded on the AE eCRF.

10.5.2. Vital Signs

Vital signs will include:

- Body temperature (°C or °F)
- Systolic and diastolic blood pressure. Pulse rate should be measured after the patient has been in a supine or sitting position for 5 minutes. Blood pressure should be assessed on the same arm throughout the study.

10.5.3. ECOG Performance Status

The ECOG performance status ([Oken, 1982](#)) will be assessed at Screening to determine eligibility of the patient and also during the study as indicated in the SoA ([Appendix 4](#)).

10.5.4. Clinical Safety Laboratory Assessments

Clinical laboratory tests (hematology and serum chemistry) will be performed by the sites' local laboratories and conducted at times specified in the SoA ([Table 6](#)). More frequent assessments may be performed if clinically indicated, or at the Investigator's discretion and these should be recorded on the eCRF.

Hematology and complete serum chemistry panel may not be repeated on C1D1 if performed within \leq 7 days and those results are within required levels as specified in the protocol.

Table 6: Clinical Safety Laboratory Tests

Hematology		
Hemoglobin	WBC (with differential)	Platelet count
Serum Chemistry		
Sodium	Creatinine	ALT
Potassium	Glucose	AST
Chloride	Calcium	Alkaline phosphatase
Bicarbonate	Phosphate	Total bilirubin ^a
BUN/urea	Magnesium	Total protein
Creatine kinase	LDH	Albumin
Uric acid		

^aIf the total bilirubin concentration is >1.5 times ULN, total bilirubin should be differentiated into the direct and indirect bilirubin.

Blood chemistry will be analyzed at each study center by a certified laboratory. The Investigator or designee will review the laboratory report after receipt of the results and assess the clinical significance of all abnormal values. Results must be reviewed prior to dosing and appropriate action taken for any clinically significant abnormal values.

The Investigator or designee will review the laboratory report to assess the clinical significance of all abnormal values. Results must be reviewed prior to dosing and appropriate action taken for any clinically significant abnormal values.

At any time during the study, abnormal laboratory values that are clinically significant (e.g., require dose modification and/or interruption of study treatment, lead to clinical signs or symptoms, or require therapeutic intervention), whether specifically requested in the protocol or not, must be documented on the AE eCRF.

If any abnormal laboratory value or test result constitutes an AE, then these must be recorded on the AE eCRF. Values will be documented in the eCRF until stabilized, or the laboratory value returns to a clinically acceptable range (regardless of relationship to study treatment) or baseline. Any laboratory value that remains abnormal at the EoT visit that is considered clinically significant will be followed according to accepted medical standards for up to 30 days or until resolution of the abnormality or return to baseline levels. For lab parameters included in the CTCAE, toxicity will be assessed using the NCI CTCAE, v. 5.0.

Karyopharm must be provided with a copy of the laboratory certification and normal ranges for each parameter measured. In addition, if at any time a patient has laboratory parameters obtained from a different outside laboratory, Karyopharm must be provided with a copy of the certification and normal ranges for that laboratory.

10.5.5. Adverse Events and Serious Adverse Events

Detailed information related to the collection and reporting of AEs and SAEs in Section 11.

All AEs will be reported by the patient (or, when appropriate, by a caregiver, surrogate, or the patient's legally authorized representative).

The Investigator and any qualified designees are responsible for detecting, documenting, and recording events that meet the definition of an AE or SAE and remain responsible for following up AEs that are serious, considered related to study treatment or study procedures, or that caused the patient to discontinue study drug (Section 11.1.2).

10.5.6. Pregnancy Testing

Pregnancy testing will be performed only for females of childbearing potential as indicated in the SoA. A negative serum human chorionic gonadotropin (hCG) pregnancy test must be obtained at Screening (within 3 days before selinexor administration). A urine hCG test is allowed if serum hCG test is not available. Pregnancy testing may be performed if clinically indicated during the study.

10.6. Other Assessments

10.6.1. Collection of Information on Antineoplastic Therapy

Information on any antineoplastic therapies planned to be used or used after discontinuation of study treatment will be collected.

10.6.2. Telephone Contacts

A telephone call will be performed at C1D3 and at the Safety Follow-up. The purpose of this telephone call with the patient is to evaluate supportive care medications, concomitant medications, and AEs, and to adjust supportive care as appropriate. After discontinuation of study treatment, follow-up phone calls will be performed after 30 days after EoT visit and every 3 months until 12 months, start of new therapy, withdrawal of consent to assess the survival status, and collect information on any antineoplastic therapies used after discontinuation of study treatment.

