Patients will be followed for survival after the end of treatment (EoT) visit every 3 months for 12 months, or until withdrawal of consent, death, or the end of study (i.e., when the last patient in the study has been followed up on study treatment for at least 1 year, or completed at least 6 months of survival follow-up period after their last dose of study treatment, has withdrawn consent, has died, or has been lost to follow-up), whichever occurs first. End of treatment imaging will be performed ≤ 28 days after treatment discontinuation for patients who discontinue for reasons other than PD if their previous scan was performed >3 weeks before EoT.

After discontinuation of study treatment, patients will also be followed for safety 30 days after EoT and then every 3 months for 12 months and for PFS approximately every 3 months after EoT visit until PD, death or initiation of the subsequent anti-melanoma treatment (if a patient discontinues from the treatment due to reasons other than PD).

Statistical Methods:

CCI

Analysis Populations:

The modified intent-to-treat (mITT) population will consist of all patients who receive at least one dose of any study treatment.

The safety population will include all enrolled patients who receive at least 1 dose of both study drugs.

Efficacy Analyses:

The primary efficacy endpoint of ORR (proportion of patients who achieve CR or PR) will be analyzed for each arm separately on the modified intent-to-treat (mITT) population which consists of all enrolled patients who received any study treatment. Estimated ORR with 95% confidence interval (CI) will be summarized for each arm.

Analyses of other efficacy endpoints will be specified in Section 12 of the protocol and the Statistical Analysis Plan (SAP)

Safety Analysis:

Continual monitoring of safety data will be performed by the independent Data Safety Monitoring Board (DSMB). Adverse events and concomitant medications will be coded according to medical dictionary for regulatory activities (MedDRA) and WHO Drug, respectively. Safety analyses will be performed on the Safety Population and will be presented by actual treatment arm.

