3.2. Schedule of Assessments

Table 1: Schedule of Assessments for Study XPORT-MEL-033 (42-Day Cycle)

Activity/Assessment	Screening ^a D -28 to -1	Cycles* 1			Cycles* ≥ 2			EoT Visit ≤ 28 Days Post-Treatment Discontinuation	Follow-up Visit ^b	
		D1	D3±2D	D15/D29 ±3D	D1	D3±2D	D15/D29 ±3D		30 days after EoTVisit +7D	Every 3 months until 12 months ±14D
Procedures										
Informed Consent	X									
Inclusion/Exclusion	X									
Demographics	X									
Medical history	X									
Concomitant Medications Review	X	Continuous					X	X	X	
Prior Melanoma Therapy	X									
Eligibility confirmation by Sponsor ^c	X									
ECOG Daily Living Performance Score	X	X		X						
Nutritional Counselling	X	Throughout, as needed								
Vital signs including weight	X	X		X			X			
Physical Exam – full	X						X		X	
Physical Exam – symptom directed		X		X				X		
Adverse Events ^d		Continuous								
Telephone contact ^e			X					X	X	
Collection of information regarding antineoplastic therapy after EoT								X	X	
Laboratory										
Hematology and Serum Chemistry	X	X		X	X		X	X		

Activity/Assessment	Screening ^a	Cycles* 1			Cycles* ≥2			EoT Visit	Follow-up Visit ^b	
		D -28 to -1	D1	D3±2D	D15/D29 ±3D	D1	D3±2D	D15/D29 ±3D	≤28 Days Post-Treatment Discontinuation	30 days after EoTVisit +7D
LDH	X	X			X			X		
Pregnancy test ^f	X	X						X	X	
CCI										
Drug Administration										
Selinexor		Selinexor will be administered once weekly (Days 1, 8, 15, 22, 29, 36 of 42-day cycle)								
Pembrolizumab		Pembrolizumab will be administered on Day 1 once every 6 weeks								
Anti-tumor Activity										
Tumor assessment by CT or MRI Scan	X	Tumor assessment will be performed every 9 weeks for 6 months, then every 3 months thereafter						X		

CT = computed tomography; D = day; ECOG = Eastern Cooperative Oncology Group; EoT = end of treatment; FU = follow-up; hCG = human chorionic gonadotropin; LDH = lactate dehydrogenase; MRI = magnetic resonance imaging; PDn = pharmacodynamics

* Cycles are 6 weeks in length.

^a Procedures that are performed as part of standard of care should not be repeated if they are within the screening window and are done prior to signing the ICF.

^b After discontinuation of study treatment for reasons other than PD, disease assessments should continue to be performed every 3 months until progression, start of new therapy or withdrawal of consent.

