^c Eligibility form with past melanoma care, length of treatment, and best response will be reviewed and approved by Sponsor prior to randomization.

^d AEs are recorded after first dose of study treatment and at any time the patient communicates an AE upon inquiry during each visit or phone call, or an AE is assessed by the Investigator, up until 30 days after EoT.

^e Telephone contact will be made on C1D3 to evaluate supportive care medications, concomitant medications, and adverse events, and to adjust supportive care as appropriate. After discontinuation of study treatment, follow-up phone calls will be performed 30 days after EoT visit and every 3 months until 12 months documenting start of new therapy and survival status.

^f Female patients of childbearing potential must have a negative serum hCG pregnancy test within 3 days prior to first study dose on C1D1. A urine hCG test is allowed if serum hCG test is not available.

CCI

CCI

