6.2. End of Treatment

The end of treatment (EoT) visit will occur \leq 28 days post-treatment discontinuation. After discontinuation of study treatment, patients will be followed for PFS approximately every 3 months after EoT visit until PD, death or initiation of the subsequent anti-melanoma treatment (if a patient discontinues from the treatment due to reasons other than PD), and for survival every 3 months after end of treatment visit for 12 months or until withdrawal of consent, death, or the end of study (i.e., when the last patient in the study has been followed up on study treatment for at least 1 year or

completed at least 6 months of survival follow-up period after their last dose of study treatment, has withdrawn consent, has died, or has been lost to follow-up) whichever occurs first.

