4.3. Secondary Efficacy Endpoints

4.3.1. Definition of Secondary Efficacy Endpoints

Table 4-1 are the secondary efficacy endpoints:

Table 4-1 Efficacy Endpoints and Definitions

Endpoint	Definition
Secondary Endpoints	
Progression-free survival (PFS)	Duration of time from date of first study treatment until the first date that PD assessed by RECIST 1.1 is objectively documented or death due to any cause. Refer to Table 4-2 for details on PFS outcome status (PFS event vs. censored) and censoring definitions.
Overall survival (OS)	Duration from the date of first study treatment until death due to any cause. If death event did not occur during the follow-up period, the patient is censored at the date of discontinuation from the study (i.e. withdrawal of consent), or date of last participating visit (e.g., a telephone contact with patient status being alive) on or before database cutoff date, whichever occurs first.
Complete response rate (CRR)	Proportion of patients who achieved a CR per RECIST 1.1
Duration of response (DOR)	Duration of time from first meeting CR or PR measurement criteria (whichever occurs first) until the first date that PD recurrence is objectively

	documented or death due to any cause. Responses are assessed per RECIST 1.1.
	Refer to Table 4-2 or details on the outcome and censoring definitions.
Disease control rate (DCR)	Proportion of patients who have a response of CR, PR, or SD ≥ 12 weeks. Responses are assessed per RECIST 1.1.

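### Protocol Section 10.6.2 lists start of new therapy as an end point of the survival calls, contradicting Section 6.2, the synopsis and SoA footnote e; followed literally, it could lose OS deaths after a switch

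*Protocol*

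**What the plan says.** Four places in the protocol govern contact after treatment ends, and the SAP sets the OS censoring date.

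- **Protocol 10.6.2 (Telephone Contacts).** After the 30-day call, calls run "every 3 months until 12 months, start of new therapy, withdrawal of consent to assess the survival status". The same sentence gives them a second task, to "collect information on any antineoplastic therapies used after discontinuation of study treatment".
- **Protocol 6.2 (End of Treatment).** Patients are followed "for survival every 3 months after end of treatment visit for 12 months or until withdrawal of consent, death, or the end of study". New therapy appears in that sentence only in the PFS clause, where follow-up runs "until PD, death or initiation of the subsequent anti-melanoma treatment".
- **Protocol 3.1 (Synopsis).** The survival rule is the same: patients are "followed for survival after the end of treatment (EoT) visit every 3 months for 12 months, or until withdrawal of consent, death". Study closure is the one remaining stop there, as in Section 6.2.
- **Protocol 3.2 (SoA).** Footnote e has the calls made "every 3 months until 12 months documenting start of new therapy and survival status". Footnote b applies a new-therapy stop to disease assessments, which continue "every 3 months until progression, start of new therapy or withdrawal of consent".
- **SAP 4.3.1, Table 4-1.** A patient not known to have died is censored for OS at study discontinuation or at the "date of last participating visit (e.g., a telephone contact with patient status being alive", whichever is earlier. Neither this table nor the OS definition in Protocol 12.4.1.2 censors at new therapy.

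**The concern.** Section 10.6.2 places start of new therapy between the 12-month limit and withdrawal of consent, as though all three end the calls. The calls exist to establish survival status, so a site working from that section could stop asking whether a patient is alive once another drug is started. It would also stop collecting later therapies at the first one, which defeats the call's other purpose.

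If no other contact takes place, the SAP rule puts the OS censoring date at about the switch. Switching mostly follows progression, so such censoring is potentially informative. It would also vary by site: those following Section 6.2 would supply deaths that those following Section 10.6.2 would not, within an arm of about 20 patients. Survival status that was never collected may be unrecoverable after site closure, and no choice of analysis replaces it.

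**Working it through.** **Step 1: the texts side by side**

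| Place | Does new therapy end survival contact? | Role given to new therapy |
|---|---|---|
| 10.6.2 | Yes, read literally | Listed as an end point; later therapies also to be collected |
| 6.2 | No | Ends PFS follow-up |
| Synopsis | No | Ends PFS follow-up |
| SoA footnote e | No | Recorded at the calls |
| SoA footnote b | Not addressed | Ends disease assessments |
| 6.3 | No | Ends AE reporting, not the visits |

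Section 10.6.2 stands alone. Its list also omits death and has no conjunction, which points to a misplaced PFS rule or a garbled form of footnote e.

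**Step 2: size of the effect if the rule is followed literally**

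The readable text gives no planned OS event count or power, so there is no figure to reproduce. What follows is an illustration.

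From the documents: median PFS 4.2 and median OS 14.0 months in the cited lenvatinib plus pembrolizumab study (Protocol 4.2), 20 patients per arm (6.1), and a limit of 12 months after EoT (6.2).

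Assumed: exponential PFS and residual survival; EoT at PD; new therapy 1 month after PD; 40%, 60% or 80% switch; 0-15% of PFS events are deaths; non-starters have 0.33-1.0 times the residual survival of starters; every site follows 10.6.2 literally and obtains no other survival information.

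The simplest case can be checked by hand (no deaths as first PFS event, equal residual survival).

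- Mean PFS a = 4.2 / ln 2 = 6.06 months.
- Mean residual survival m is set so that OS has median 14.0: [m·exp(-14/m) - a·exp(-14/a)] / (m - a) = 0.5, giving m of about 10.95.
- Section 6.2 rule: deaths = 20 × [1 - exp(-12/10.95)] = 20 × 0.666 = 13.3.
- Literal 10.6.2 rule, switching proportion p: deaths = 20 × {(1 - p) × 0.666 + p × [1 - exp(-1/10.95)]}, where the last bracket is 0.087.
  - p = 0.4: 20 × (0.399 + 0.035) = 8.7
  - p = 0.6: 20 × (0.266 + 0.052) = 6.4
  - p = 0.8: 20 × (0.133 + 0.070) = 4.1

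Simulating the full set of assumptions, with the Kaplan-Meier median read from each censored sample, gives:

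| Switching | Deaths per 20, Section 6.2 | Deaths per 20, literal 10.6.2 | KM median OS, literal 10.6.2 (true 14.0) |
|---|---|---|---|
| 40% | about 13 | about 9-11 | about 13-16 months |
| 60% | about 13 | about 6-9 | about 13-18 months |
| 80% | about 13 | about 4-7 | about 14-22 months |

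A variant with a mean of 1.5 months to new therapy, 15% of PFS events as deaths, and a death hazard in switchers of 1.0 or 0.6 times that of non-switchers starts from 12.8 deaths and a median of 14.0 under Section 6.2. Under literal 10.6.2 it gives 9.6-10.1, 7.9-8.5 and 6.3-6.7 deaths, and medians of 13.9-14.9, 14.3-15.8 and 15.7-17.3 months.

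**Step 3: why the median does not move one way**

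Censoring at the switch removes progressed patients, whose hazard is higher than that of patients still progression-free; this pushes the curve up. If non-starters fare worse than starters, the progressed patients left at risk are the worse ones; this pushes it down. Which effect dominates depends on quantities the documents do not give.

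**The case against.** The strongest reply is that a literal reader of Section 10.6.2 still owes the patient other contact. Section 6.3 requires follow-up 30 days after EoT and then 3-monthly for 12 months to assess patient status, with no stop at new therapy. Section 10 makes adherence to the SoA essential, and footnote e continues the calls. SAP Table 4-1 names the telephone contact only as an example of a last visit, and any death that becomes known still counts. A site that keeps to Section 6.3 or the SoA loses nothing.

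This stands, and it makes the harm conditional. It does not remove the contradiction: no passage says the SoA or Section 6.3 overrides Section 10.6.2, which is the section that describes these calls.

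Two stronger readings are tempting. A reader might infer that the sponsor chose to end OS follow-up at a switch; Section 6.2 and the synopsis say the opposite, and the wording of Section 10.6.2 looks like a slip. A reader might also infer that OS will be cut off in every patient who switches and the median inflated. The first part assumes that the Section 6.2 and 6.3 follow-up is dropped too, which nothing in the documents says. The second is not supported by the calculation, whose ranges include values below 14.0.

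**Conclusion.** The inconsistency is real and should be corrected. As worded, Section 10.6.2 contradicts three other places in the protocol and the second purpose of its own sentence.

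The effect on OS depends on sites following that section literally and not learning survival status another way. If all did so, the illustration loses about 2-4 of 13 deaths per 20 patients at 40% switching (13 less 9-11), 4-7 at 60% (13 less 6-9) and 6-9 at 80% (13 less 4-7). Fewer deaths is the consistent result across scenarios; neither the size nor the direction of the change in the median is established. Switching rates, time to new therapy and relative survival after progression are assumptions, and the 14.0 and 4.2 month medians come from another study.

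The consequence is confined to a secondary endpoint summarised descriptively by arm. OS is limited in any case by the 12-month cap, which is a separate matter. The primary ORR does not depend on these calls.

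**What to change.** In Protocol Section 10.6.2, delete start of new therapy as a stop for the survival calls, or state that it ends disease assessments for PFS only. The sentence should then say that calls continue every 3 months whether or not a new antineoplastic therapy has begun, recording each new therapy and survival status, until the end point in Section 6.2. This brings it into line with Section 6.2, the synopsis and SoA footnote e.

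The cost is one sentence, in an amendment or a clarification letter to sites. It adds no contact beyond what Section 6.2 and the SoA already require, and the SAP needs no change.
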